4.2. Experimental Design

This pilot study is a stratified interventional study that will evaluate the response of an exploratory biomarker. There will be no placebo-controlled groups, and the study main intervention will be systematically assigned to all subjects with SzNET identified by the first rs-fMRI. Patients without SzNET will not receive the study treatment and will continue their medical therapy as directed by their care team. They will be included in the required analysis for aim 2 and 5. Two specialists will assess the two post-intervention follow-up studies, the rs-fMRI#2 and the repeat EEG, providing the only blinding needed. These study design elements will ensure the technical requirements necessary to calculate the sample size required for a larger trial in EEG-negative patients with SzNET-positive and explore two important aspects of the biomarker SzNET: its correlation with the EEG response of patients and the effect size of its response to the intervention ASM.

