2.2. Scientific Rationale

Study Proposal: This is an uncontrolled two-arm open-label single-center interventional clinical trial that will be used to prepare for a full-scale randomized, placebo-controlled trial by investigating the feasibility of the study and proposed measures collection. It will explore changes in SzNET, RSNs, and EEG data, before, and after combination drug therapy with levetiracetam and phenobarbital (or a combination of two other ASM drugs (see section 4.1) and psychometric measures at 3 months after hospital discharge based on a sample of 54 patients with MSABI and DoC. Our long-term goal for this research line is to determine if SzNET are linked to epileptogenic activity in SABI to improve the endotype characterization of its DoC and better guide targeted treatments.

Rational for specific aims and outcome measures: The purpose of this study is to determine the occurrence of a specific biomarker called SzNET in patients with MSABI and investigate the effects of ASM on SzNET. The study also aims to find any correlation between EEG and SzNET in patients who experience seizures on EEG.

The study outcome measures will focus on quantifiable changes in SzNET and RSNs with therapy. It is difficult to isolate the effects of early therapy on outcomes due to the high rate of withdrawal of life sustaining therapy in the early weeks of MSABI and the potential secondary injuries. Therefore, this study will take a conservative approach and focus on quantifiable changes in SzNET and RSNs with therapy. If there are no significant changes in the networks after therapy, it may not be necessary to further investigate the relationship between SzNET and outcomes. The feasibility of collecting outcomes and trends in relation to SzNET will be tested as part of this pilot study through ICU exams and follow-up clinics, including side effects of medication, morbidity, and mortality, to identify any positive trends.

Rational for study inclusion/exclusion criteria: This study focuses on patients with brain damage severe enough to impair consciousness but with the potential to recover in the absence of epileptogenic activity. The inclusion criteria have been chosen to identify patients with this level of brain damage.

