All patients with an identified SzNET in rs-fMRI#1 will be included in the intervention group. Within one and six days after the first scan, the care team will decide and start the intervention with two ASM agents from the list. The intervention phase occurs between rs-fMRI#1 and the day of follow-up rs-fMRI#2 and repeated EEG. The intervention is considered complete and the follow-up tests can be done if the patient received the study ASM for at least 72 hours after the loading dose start, and the second scan must be done within 72 hours of the last intervention ASM dose. The treatment protocol can continue up to a maximum of ten days to improve the opportunity to schedule the scan. Thus, the rs-fMRI #2 must be done at a time between 73h and 312h (the fourth and thirteenth days) after the intervention phase starts, and the subject can still be receiving the intervention at that time.

Once the rs-fMRI #2 is obtained, the subject's ASM treatment can be continued or changed for clinical reasons depending entirely on the care team's decision, then it will not be considered part of the study's intervention phase or be related to the research team.

The intervention aims to validate the epileptogenic background of the SzNET by using an ASM that is known to be effective. We expect the intervention will influence the improvement of the SzNET. We hypothesize that the intervention will selectively modulate the networks caused by epileptogenic activity, while having less to no impact on abnormal networks caused by other phenomena.

The length of the intervention is designed to be adequate for pharmacological modulation of epileptogenic activity. The six-day time frame between the minimum and the maximum treatment protocol time facilitates a window for the rs-fMRI schedule that is a realistic schedule time frame in the ICU.

From the different ASM options the key intervention and first option to be considered as intervention will be phenobarbital + levetiracetam. This specific ASM combination will be communicated clearly to the ICU care teams as the first line of the study intervention. However, for clinical reasons the care team will be free to select any combination of two or more study listed ASM regimens. On day two of maintenance dosing, the phenobarbital serum level will be measured if it is one of the selected medications, and a new loading dose will be given to aim for a level of 40mcg/ml.

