 - ◆ Rs-fMRI does not require contrast agents to be administered.
 - ◆ In case of tattoos with suspected high levels of ferromagnetic compounds cold compresses can be applied to prevent heating.
 - ◆ Transportation through the hospital to perform the MRI scan can be associated with mechanical risks and support devices malfunction. Trained personnel is in charge of the process, which is supervised by a physician.

○ SzNET Stratification of rs-fMRI

- SzNET (-): with EEG (+) or EEG (-).
 - ◆ N=32
 - ◆ No protocol Intervention-driven, combined ASM is administered.
 - ◆ They will not receive the second fMRI.
 - ◆ They will only be followed at the 3 months post discharge visit if they are scheduled to one of the NSICU Post-Discharge clinics.
 - ◆ MRI scan transportation related AE Review.
- SzNET(+): with EEG(+).
 - ◆ N=11
 - ◆ Proceed with combined ASM Intervention.
 - ◆ Intervention **must** start within 1 to 6 days after enrollment.
 - ◆ AE Review.
- SzNET(+):with EEG(-)
 - ◆ N=11
 - ◆ Proceed with combined ASM Intervention.
 - ◆ Intervention **must** start within 1 to 6 days after enrollment.
 - ◆ AE Review.

○ Study team will inform the family of the rs-fMRI results and upload the official report to EPIC.

Intervention start (Days 1-6 from Enrollment)

- **Clinical Care Team** will choose the intervention regimen.
 - If participant was already on **two** of the protocol-approved ASM, the participant will be required to start the intervention by administering the protocol-driven loading dose infusions outlined for

each of the combined ASMs, or by administering the loading dose for any of the other 5 listed ASM options. A third option in this case is to administer protocol-driven loading dose of one of the current medications and add another of the 5 ASM loading dose and maintenance regimen.

- If participant was already on **one** of the protocol-approved ASM, the participant will be required to start the intervention by administering the protocol-driven loading dose outlined for the ASM that the participant was previously receiving *along with* another protocol-driven ASM loading dose from the ones listed on the protocol.
- If participant **was not receiving any** of the protocol approved ASM, the participant will be administered a loading dose of two of the 5 protocol approved ASM.
- If the clinical care team does not want to use a combination of two of the 5 protocol-approved ASMs, they will not be enrolled into the study.

- **Research Team** will

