8.3. Aim-Specific Plans

Plans for Aim 1.

Aim 1 is to obtain preliminary data about the degree of improvement of seizure networks (SzNET) in moderate to severe acute brain injury (MSABI) patients after intervention's antiseizure medication (ASM).

Aim 1a

Measure the improvement of the SzNET total volume in MSABI patients after the intervention's ASM. The primary outcome of interest is the SzNET total volume median before and after the intervention's ASM in the target population.

H_0 : there will be no difference in the SzNET total volume median in MSABI patients before and after the intervention's ASM.

H_1 : SzNET total volume median in MSABI patients before ASM will be smaller than after the intervention's ASM.

Aim 1b

Measure the improvement of the SzNET power spectrum in MSABI patients after ASM. The outcome of interest is the SzNET power spectrum median before and after ASM in the target population.

H_0 : there will be no difference in the SzNET power spectrum median in MSABI patients before and after the intervention's ASM.

H_1 : SzNET power spectrum median in MSABI patients before ASM will be higher than after ASM.

We plan to recruit 11 patients with SzNET+EEG+ and 11 subjects with SzNET+EEG-. Therefore, 22 subjects with measurements before and after the intervention's ASM will be used in Aims 1a and 1b. We will fit linear regression models with dependent variables as follows. We calculate the changes of the SzNET total volume and the SzNET power spectrum before and after the intervention's ASM and use them as the primary dependent variables. Due to the small number of subjects, we only include an intercept to represent the mean difference before and after the intervention's ASM in the model, and we use the t-test statistic to test whether the intercept is equal to zero for Aims 1a and 1b. Moreover, we may consider demographic variables and pre-intervention EEG status (EEG+ or EEG-) if necessary.

Plans for Aim 2.

Estimate the frequency of EEG- and EEG+ patients presenting SzNET. The outcomes of interest are the proportions and differences of proportions of patients with SzNET among EEG- and EEG+ patients in this clinical setting.

For aim 2, we sequentially recruit SzNET+ subjects until the number of subjects in either SzNET+EEG+ or SzNET+EEG-first reaches 11 subjects. We will calculate the proportions of patients with SzNET among EEG- and EEG+ patients. and use the two-proportion Z-test to test their difference.

Plans for Aim 3.

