8.4. Planned Interim Analyses

No interim analyses will be performed.

9. Sample Size Rationale

There is no preliminary data for effect size estimation using the paradigm and patient population suggested in this study. In Aim 1, a paired t-test is used to test measurement differences before and after ASM. A effect size 0.806 can be detected for a 1-sided test at a power of 80% and a Type I error at 0.05 with the total of 11 subjects before and after ASM. In Aim 4, a transformed Z-test is used to test correlation between two variables. A correlation size 0.506 can be detected for a 1-sided test at a power of 80% and a Type I error at 0.05 with the total of 22 subjects.

10. Data Capture and Database Management

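### Scan 1 both selects patients and serves as their baseline, with no untreated rescan, so the Aim 1 change does not isolate a drug effect and cannot stand in for a between-arm effect

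*Combined protocol and SAP*

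**What the plan says.** Section 4.1 puts every patient with SzNET on rs-fMRI#1 into the intervention group. For SzNET- patients, section 6 says: "They will not receive the second fMRI". Section 4.2 states that there is no placebo group.

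For the analysis, section 8.3 fits a model with an intercept only, and "we use the t-test statistic to test whether the intercept is equal to zero for Aims 1a and 1b". It adds: "Therefore, 22 subjects with measurements before and after the intervention's ASM will be used in Aims 1a and 1b". Section 9 describes the same comparison: "In Aim 1, a paired t-test is used to test measurement differences before and after ASM".

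Three places say what the result is for:

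- Section 4.1: "The intervention aims to validate the epileptogenic background of the SzNET by using an ASM that is known to be effective".
- Section 2.2: "If there are no significant changes in the networks after therapy, it may not be necessary to further investigate".
- Section 4.2: "These study design elements will ensure the technical requirements necessary to calculate the sample size required for a larger trial". That larger trial is in EEG-, SzNET+ patients. The same sentence lists the effect size of the SzNET response as something to explore.

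No repeat baseline scan, test-retest figure or correction for regression to the mean appears in the plan.

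**The concern.** Every patient in Aim 1 was above the detection limit on scan 1. On scan 2 the measured network can persist, shrink or vanish. A patient who was SzNET- on scan 1 and positive later is never seen. With any measurement noise or day-to-day fluctuation, the group selected for being high is expected to be lower when measured again. Spontaneous recovery between the scans would add to that fall; true worsening could offset it.

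Two things are at stake. A significant Aim 1 result could be read as support for an epileptogenic origin of SzNET when selection alone may have produced it. And if the before-after effect size were used as the between-arm effect of the placebo trial, that trial would be too small.

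**Working it through.** **The plan's own figure.** Section 9: "A effect size 0.806 can be detected for a 1-sided test at a power of 80% and a Type I error at 0.05", with 11 subjects. For a one-sample t-test on paired differences, power is 1 − F(t₀.₉₅,ₙ₋₁; n−1, d√n), where F is the noncentral t distribution. With n = 11, 80% power needs d = 0.806, so the figure reproduces. It uses 11, whereas 8.3 uses 22; at n = 22 the one-sided figure is 0.548. The arithmetic is sound; the issue is what the difference measures.

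**Inputs.** Section 5.1 gives positivity of 30% (EEG-) and 67% (EEG+), and 11 SzNET+ patients per stratum. The documents give neither the retest correlation ρ nor the between-patient spread. Both are assumed: ρ from 0.5 to 0.95, log SD 0.5 or 1.0. There is no drug effect and no time trend.

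**A case that can be checked by hand.** Let the burden z be standard normal and SzNET+ mean z > c. With p the share positive and λ = φ(c)/p, the expected fall is (1−ρ)λ. The variance of the change is (1−ρ)²(1 + cλ − λ²) + (1−ρ²). At ρ = 0.7:

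- EEG-: p = 0.30, c = 0.524, λ = 1.159. Fall = 0.3 × 1.159 = 0.348. Variance = 0.09 × 0.264 + 0.51 = 0.534, SD 0.731. Standardized fall 0.348/0.731 = 0.48.
- EEG+: p = 0.67, c = −0.440, λ = 0.541. Fall = 0.162. Variance = 0.09 × 0.470 + 0.51 = 0.552, SD 0.743. Standardized fall 0.22.

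**Other outcome shapes.** Simulation of 20,000 trials per cell, 11 + 11 patients. Entries are the percentage rejecting zero at nominal 5%, one-sided / two-sided. The last column is the spurious standardized fall at ρ = 0.7, EEG- / EEG+.

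| Outcome shape | ρ 0.5 | ρ 0.7 | ρ 0.9 | ρ 0.95 | Fall |
|---|---|---|---|---|---|
| Burden z itself | 66 / 53 | 46 / 33 | 22 / 14 | 15 / 9 | 0.47 / 0.22 |
| Linear excess over threshold, else 0 | 36 / 25 | 24 / 15 | 13 / 8 | 10 / 6 | 0.27 / 0.13 |
| Log-normal, 0 if SzNET-, log SD 1.0 | 44 / 33 | 33 / 23 | 21 / 13 | 17 / 10 | 0.29 / 0.09 |
| Same, log SD 0.5 | 80 / 70 | 66 / 53 | 44 / 29 | 32 / 18 | 0.61 / 0.28 |
| Log-normal excess over threshold, log SD 1.0 | 21 / 13 | 14 / 8 | 8 / 5 | 7 / 4 | 0.13 / 0.04 |
| Same, log SD 0.5 | 28 / 19 | 19 / 11 | 10 / 6 | 8 / 6 | 0.20 / 0.08 |
| Log-normal, no drop to 0, log SD 1.0 | 32 / 22 | 21 / 13 | 11 / 7 | 9 / 5 | 0.19 / 0.06 |
| Same, log SD 0.5 | 48 / 36 | 32 / 22 | 16 / 10 | 12 / 7 | 0.34 / 0.13 |

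Repeat runs move the largest entries by about one point, so the range is about 7% to 81% one-sided and 4% to 69% two-sided.

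**Responders.** In the shapes where a network can vanish to zero, about 11% to 56% of patients pass the 0.5 TVR threshold by chance. If nothing drops to zero, the share is 0% to 39%. Aims 3 and 4 use this threshold to split patients.

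**Drift.** A true fall of 0.3 SD without drug would by itself give 39% one-sided rejection at n = 22.

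**What it could do to a sample size (illustration).** Per arm, n = 2(1.96 + 0.84)²/d² = 15.7/d² (two-sided 5%, 80% power). Suppose the EEG- stratum shows 0.806. At face value, 15.7/0.650 gives 25 per arm. Subtracting a spurious 0.13 leaves 0.676 and 35 per arm; subtracting 0.61 leaves 0.196 and 409 per arm.

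**The case against.** The case for the plan is substantial.

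- **The null in 8.3 is about before and after, not drug.** A fall in the selected group is a real before-after difference in measured SzNET, so rejecting zero is not an error against that null. This stands: the fault lies in reading the result as a drug effect, which 4.1 does.
- **The plan is modest elsewhere.** It calls itself uncontrolled and a pilot, describes the Aim 1 estimate as preliminary, says in 2.1 that a response would not be definitive proof of epileptogenic cause, plans 95% intervals in 8.1, and names a placebo-controlled trial as the next step. None of this addresses selection on the baseline scan or corrects the language in 4.1 and 4.2.
- **The size is unknown.** This stands. The rates depend on ρ, on the outcome shape, especially whether volume jumps to zero at the detection limit, and on sidedness, which 8.3 does not state (section 9 is one-sided).
- **Section 4.2 need not mean the before-after mean.** A reader might infer that it becomes the between-arm effect. The text does not expressly say so; sizing from SD, prevalence and attrition also fits the sentence.
- **Section 2.2 is not a rule to proceed on significance.** It describes only a possible stop if nothing changes significantly. Even so, a fall due to selection makes that stop less likely.
- **Time variables are recorded.** Section 4.3 labels several as confounders but assigns them to no aim. Adjusting for them would not remove regression to the mean.

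The H1 for Aim 1a is also written in the opposite direction, with volume smaller before than after. Read literally, a one-sided test would look the other way. This conflicts with the aim of improvement and with Aim 1b; it needs reconciling and is no safeguard.

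**Conclusion.** The concern holds as a matter of validity and interpretation. With selection and baseline on the same scan and no untreated rescan, a stable condition and reliability below 1 imply an expected fall with no drug effect. The Aim 1 test therefore does not test an ASM effect, and the before-after effect size is not a valid between-arm effect.

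Under the stated assumptions, rejection with no drug effect runs from near nominal (7% one-sided, 4% two-sided) to very high (81% and 69%). The bias is larger in EEG- than in EEG+, because fewer are selected: at ρ = 0.7 the spurious standardized fall in EEG- is about 0.13 to 0.61.

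A reader might go further and conclude that SzNET is bound to fall, or that the test is badly anti-conservative whatever the scanner's reliability. The documents support neither. Worsening could offset the fall, and with high reliability and a volume that shrinks smoothly to zero the excess is small. The pilot can still inform SzNET prevalence, enrollment, attrition and variability.

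**What to change.** - **8.3:** Report the Aim 1 change with its 95% interval, overall and by EEG stratum, as a before-after change. State that rejecting zero is not evidence of an ASM effect. State the sidedness and reconcile the direction of H1 for Aim 1a.
- **4.2 and 9:** State that sizing of the placebo trial will use SzNET prevalence, attrition and the residual SD of scan-2 TV and PS given scan 1 in the EEG- stratum. State that the effect will be a prespecified worthwhile between-arm difference, not the before-after mean. Give the imprecision of that SD. With n = 10 and 8 residual degrees of freedom, the 95% limits are √(8/17.53) = 0.68 to √(8/2.18) = 1.92 times the estimate, assuming normal residuals.
- **4.1 and 2.2:** Soften the validation and significance language to match.
- **Plots** of change against time from injury and scan interval are worth showing, labelled descriptive. They do not correct regression to the mean.

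The cost is wording and a weaker headline claim; no extra scans. This changes what may be concluded but does not remove the bias. In the same simulations, a second pre-treatment scan used as baseline brought one-sided error to 4.6% to 5.4%, but it would not deal with spontaneous recovery. A concurrent untreated comparison (4.5% to 4.9%) deals with both, and the planned placebo trial will supply that.

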4.3. Measurement Design

Table 2. Variables of interest: their occasions of evaluation, their uses for the aims, their roles in the study

Variables within Domains	Scale ¹	Occasions ²	Aims ³	Main Roles
Identifiers				
Participant's unique ID	nominal	all	all	identifier

Intervention	categorical	E	All, except aim 2	intervention
Clinical Health Profile				
Spontaneous ventilation	Binary	E, 2	Aim 1	Exploratory uses
Glasgow Coma Scale (GCS)	Ordinal 3-15	S, E, 2	--	Screening
weight	kg	E	--	dosing
height	cm	E	--	dosing
body mass index (BMI)	kg/cm ²	E	--	dosing
body surface area (BSA)	kg/m ²	E	--	dosing
Supratentorial decompressive craniectomy	Binary	S, E, 2	--	Exploratory uses
age	decimal yrs	S	--	screening
sex	categorical	S	--	Exploratory uses
Pre-MSABI BIS (appendix a)	Ordinal 0-100	S	--	screening
Medical Records				
Presumed etiologies of disorder of consciousness	Categorical	S	--	screening
co-morbidities list	nominal	S	--	screening
Clinical tests				
2HELP2B Score	Ordinal 0-7	S	--	Exploratory uses
pre-intervention EEG status (EEG monitoring Seizures)	Binary	E	All	classification
Research tests				
SzNET presence	Binary	E	All	Classification and primary outcome
Total Volume (TV)	continuous	2	Aim 1a	primary outcome
Total Volume Reduction (TVR)	continuous	2	Aim 1a, 3, 4	primary outcome
Power Spectrum (PS)	continuous	2	Aim 1b	primary outcome
Power Spectrum Improvement (PSI)	continuous	2	Aim 1a, 3, 4	primary outcome
Typical RSN improvement	Binary	2	Aim 4	Secondary outcome
EEG improvement	Binary	2	Aim 3	Secondary outcome
Protocol Time Frames				
Days of antiseizure medication	Days (discrete)	2	-	Confounder
Time from MSABI to rs-fMRI#1 (days)	Days (discrete)	2	-	Confounder
Time from MSABI to rs-fMRI#2 (days)	Days (discrete)	2	-	Confounder
Time from MSABI to treatment protocol start (days)	Days (discrete)	2	-	Confounder
Time from enrollment to rs-fMRI#1	Days (discrete)	2	-	Secondary outcome
Questionnaires/survey instruments⁴				
Anxiety: PROMIS Emotional Distress—Anxiety—Short Form (appendix H)	Ordinal 7-35	3	Aim 5	Exploratory outcome

Depression: Neurological Disorders Depression Inventory for Epilepsy (NNDI-E) (appendix I)	Ordinal 6-24	3	Aim 5	Exploratory outcome
Quality of Life: QOLIE-10-P (appendix J)	Ordinal 1-10	3	Aim 5	Exploratory outcome
Telephonic Montreal Cognitive Assessment (appendix K)	Ordinal 0-15	3	Aim 5	Exploratory outcome
ASM toxicity: Liverpool adverse event profile test (appendix L)	Ordinal 19-76	3	Aim 5	Exploratory outcome
Safety Monitoring		Any time (AT) After E		
Adverse event related with the transportation to the MRI scan.	Ordinal 1-5	AT after E	-	safety monitoring
Adverse event related with the transportation to the MRI scan. Description	nominal	AT after E	-	safety monitoring
Adverse event related with the intervention	Ordinal 1-5	AT after E	-	safety monitoring
Adverse event related with the intervention. Description	nominal	AT after E	-	safety monitoring
Dropout	binary	AT after E	Aim 6	Secondary outcome
Dropout date	ordinal	AT after E	Aim 6	Secondary outcome
Dropout cause	nominal	AT after E	-	safety monitoring
Feasibility				
Informed consent acceptance	Binary	E	Aim 6	confounder

¹ Units of measurement or the scale.

² Occasions of evaluation or retrieval: **S** = screening, **E** = enrollment, **2** = rs-fMRI#2, **3** = 3 months

³ The specific aims in which the variable will play a role in data analyses.

⁴ will be collected by one of the NSICU Post-Discharge clinics.

In Table 2, the treatment regimens must include two from:

6. Phenobarbital
7. Levetiracetam
8. Lacosamide
9. Valproate
10. Fosphenyton

In Table 1, the allowed Presumed etiologies of disorder of consciousness are:

1. Hypoxia/anoxia (i.e., respiratory arrest with preserved circulation)
2. Hypoxic-ischemic injury (i.e., cardiac arrest).
3. Ischemic stroke.
4. Intracerebral hemorrhage.
5. Subarachnoid hemorrhage.
6. Subdural hemorrhage
7. Epidural hemorrhage
8. Traumatic brain injury (penetrating).
9. Traumatic brain injury (non-penetrating).
10. Venous sinus thrombosis/cortical vein thrombosis

Baseline Variables:

- The Medical record domain variables will focus on retrieving information to screen patients and verify inclusion-exclusion criteria. Thus, the previous history of epilepsy and neurological problems that could lead to functional dependence greater than expected for age are relevant confounders that will be avoided in this pilot trial. The presumed etiology of DoC are the inclusion criteria, and we expect to evaluate the rs-fMRI for exploratory purposes in subgroup analysis. Glasgow coma scale GCS is a baseline variable that will be collected in more time points.
- The presence of SzNET will classify the patients that will receive intervention corresponding to the protocol and those that will only continue medical treatment according to care team indications in case of the presence or the absence of SzNET in the first MRI, accordingly. Outcomes will be reported as proportions and differences of proportions of patients with SzNET among EEG- and EEG+.
- Surface EEG monitoring pre-intervention (Seizures) is a binary variable collected from the total available surface EEG monitoring before rs-fMRI#1 with EEG+ and EEG- as possible values and retrieved by the investigators from the medical record or direct communication with the Epileptologist, which later must be supported in the medical records. EEG+ is defined as surface EEG with the presence of electrographic seizure, electroclinical seizure or ictal-interictal continuum.

Outcome Variables:

Each SzNET is made of one or more BOLD signal independent components that share atypical temporal or spatial features ¹¹.

- SzNET total volume (TV) is the sum of the volumes of the SzNET independent components. The TV change from before to after the intervention is a ratio expressed as the TV reduction (TVR), and is given by:

$$TVR = 1 - \frac{\sum_{i=1}^n P_i}{\sum_{i=1}^n E_i}$$

Where P is the volume of a post-treatment SzNET, E is the spatial volume of an initial SzNET and n is the amount of SzNET in each rs-fMRI.

- Power Spectrum (PS) is the sum of the power spectrum of the SzNET independent components normalized by their spatial volumes. The PS change from before to after the intervention is a ratio expressed as the PS improvement (PSI) and is given by:

$$PSI = 1 - \frac{\sum_{i=1}^n [P \int_{6.78}^{27.12} f(s)]_i}{\sum_{i=1}^n [E \int_{6.78}^{27.12} f(s)]_i}$$

Where F(S) is the power spectrum curve.

- EEG improvement Binary variable categorized in "with improvement" or "without improvement", obtained by expert's overall qualitative assessment comparing the follow-up study EEG and the clinically indicated EEG considered at the enrollment time. This qualitative assessment will be based on the EEG's background and the presence of electrophysiological signs of ictal or interictal activity.

These signs are described by the American Clinical Neurophysiology Society as:

- o Epileptiform Discharges
- o Rythmic and periodic patterns
- o Electrographic and electroclinical seizures.
- o Ictal-interictal continuum.

It will be used to investigate the association in patients with a clear improvement of their SzNET. Such improvement will be defined as more than 0.5 TVR or 0.5 PSI threshold.

- RSN improvement is a binary variable collected by the study coordinator based on clinical records of the rs-fMRI#2, taking into consideration the spatial and temporal features and the number of canonical RSN

observed in the rs-fMRI#2. It will be used to investigate association in patients with a clear improvement of their SzNET; such improvement will be defined as more than 0.5 TVR or 0.5 PSI threshold.

- All the variables listed as exploratory will be studied for association in patients with clear improvement of their SzNET, such improvement will be defined as more than 0.5 TVR or 0.5 PSI threshold.

-

Comments regarding extended age range: 18 months to 70 years of age had heterogeneity of brain function related to both neurodevelopment and old-age related degenerative processes. However, the impact of seizure on brain networks that causes suppression of consciousness is similar through these age groups. For example when seizure occurs we expect reduction in consciousness in both young and old who have either epilepsy or acute brain injury. Patient's age may have impact on the clinical outcomes and connectivity aspects of resting state networks, for that reason we will analyze seizure networks (SzNET) different to the typical resting state networks (RSN). The analytical approach to SzNET that depend mostly on the ictal activity will be quantitative, but RSN improvement is a binary variable based on experts opinion judging the presence or absence of these normal networks that are described and used for neuroprognostication across different age groups³⁰⁻³²

Safety and Feasibility Variables:

These variables will be collected as part of the safety monitoring. Some of these variables also aim to determine how practical and viable is the study design, recruitment strategies, and participant retention in our institutional actual context. By closely monitoring the enrollment rate, which measures the efficiency of the recruitment process, and the dropout rate, which indicates the probability of the participants to continue with the study. Valuable insights can be gained regarding the feasibility of conducting a similar study on a larger scale. This findings will provide crucial information for refining future study protocol and improving recruitment and retention strategies to ensure the successful implementation of future research projects with similar conditions.

5. Study Participants

